4.4.2. Visit naming Conventions

The electronic Case Report Form (eCRF) visit label will be used to classify the assessments.

4.4.3. Visit Windows

The visit windows as defined in [Section 15.5](#) will be applied to all endpoints.

4.4.4. Unscheduled Visits

Unscheduled visit measurements will be used in the analysis on efficacy variables and will be included in the by-visit summaries for the safety variables if they are re-allocated to scheduled visits according to the visit window definitions in [Section 15.5](#).

4.4.5. Display of Data Summary and Analysis

Continuous variables will be summarized using descriptive statistics, including the following: sample size (n), mean, standard deviation (SD), median, first quartile (Q1), third quartile (Q3), minimum and maximum for each treatment group.

All mean, Q1, Q3 and median values will be formatted to one more decimal place than the measured value. SD values will be formatted to two more decimal places than the measured value. Minimum and maximum will be formatted to the same number of decimal places as the measured value.

95% confidence intervals (CIs) will be two-sided and displayed to the same level of precision as the statistic they relate to. If an estimate or a CI is not estimable, it will be presented as 'NE'. If neither an estimate, nor its CI are estimable, it will be presented as simply 'NE', not displaying 'NE' twice.

The p-values will be two-sided and will be rounded to three decimal places. If a p-value is less than 0.001 it will be reported as '<0.001'. If a p-value is greater than 0.999 it will be reported as '>0.999'.

Categorical and ordinal data will be summarized using the counts and percentages. When count data are presented, the percent will be suppressed when the count is zero in order to draw attention to the non-zero counts. A row denoted 'Missing' will be included in count tabulations for demographics, baseline characteristics and compliance to account for missing values. No percentages will be displayed on the 'Missing' rows and the percentages on the other rows will be based on the number of non-missing observations. Unless otherwise specified, the denominator for all other percentages will be the number of subjects in that treatment within the specific analysis set of interest. All percentages will be rounded to one decimal place. The number and percentage of responses will be presented in the form xx (xx.x), where the percentage is in the parentheses. When the numerator is equal to the denominator, the percentage should be presented as (100) instead of (100.0).

All listings will be sorted for presentation in order of assigned treatment arm, study center number, patient number and date of procedure or event.

4.4.6. Baseline, study day and duration derivations

The baseline value of efficacy parameters is defined as the last available valid (non-missing) value on or prior to randomization and prior to the first dose of study medication except as noted below.

- For assessments to be completed daily during the week prior to baseline visit (e.g., sleep NRS, actigraphy parameters, sleep diary, etc.), their baseline value will be the average of 7 continuous - days of assessments (or at least 5 days if data for 7 days were not available) prior to the Visit 1 Week 0 baseline visit but after the Screening visit.
- Polysomnographic data collected at the acclimation night (Day -2) will not be used.

The baseline value of safety parameters is defined as the last available valid (non-missing) value prior to the first dose of investigational medicinal product (IMP).

If multiple valid values of a variable (efficacy or safety) exist within a same day and time is not available, the scheduled value will be used. If no scheduled value is available, then the average will be selected.

Baseline safety and efficacy results are presented in the safety and efficacy analyses.

The reference day (denoted as Day 1) for the calculation of extent of exposure and study day for AE listings will be the day of the first administration of IMP:

- Extent of exposure (see [Section 7.2.1](#))
- Study day for AE listing: AE onset date – first administration date of IMP + 1

The reference day (denoted as Day 1) for the calculation of study day of efficacy assessments will be the randomization date.

- For visit prior to randomization, study day = assessment date – randomization date.
- For visit at or after randomization, study day = assessment date – randomization date + 1.

Intervals that are presented in weeks will be transformed from days to weeks by using (without rounding) the following conversion formula:

$$\text{WEEKS} = \text{DAYS} / 7$$

Intervals that are presented in months will be transformed from days to months by using (without rounding) the following conversion formula:

$$\text{MONTHS} = \text{DAYS} / 30.4375$$

The last on-treatment value of safety parameters is the final measurement assessed during the treatment epoch (double-blind treatment period and OLE period respectively), regardless of the introduction of rescue therapy, including measurements at unscheduled visits.

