5.1 INCLUSION CRITERIA

Participants are eligible to be included in the study only if all of the following criteria apply:

Age

I 01. Participant must be 18 years of age or older, at the time of signing the informed consent

Type of participant and disease characteristics

- I 02. Participants with chronic AD that has been documented for at least 2 years before the screening visit
- I 03. Inadequate response to topical medications or otherwise candidate for systemic AD treatment
- I 04. Eczema Area Severity Index (EASI) score ≥ 12 at screening and baseline visits
- I 05. Investigator's global assessment (IGA) score ≥ 3 (on the 0 to 4 IGA scale) at the screening and baseline visits
- I 06. $\geq 10\%$ body surface area (BSA) of AD involvement at the screening and baseline visits
- I 07. Baseline pruritus NRS score for maximum itch intensity ≥ 3 (based on weekly average of daily scores during the 7 days immediately preceding baseline, or based on average of daily scores completed for 5 days (from Day -7 to Day -3 prior to baseline) for patients participating in the PSG sub-study; at least 4 ratings over the prior week/over the 5 days are required to calculate the average)
- I 08. Baseline Sleep Quality NRS score ≤ 5 (based on weekly average of daily scores during the 7 days immediately preceding baseline, or based on average of daily scores completed for 5 days (from Day -7 to Day -3 prior to baseline) for patients participating in the PSG sub-study; at least 4 ratings over the prior week/over the 5 days are required to calculate the average)
- I 09. Have been applying skin emollients (moisturizers) twice daily (once daily on areas receiving background topical medications – see [I 10](#) below and [Section 6](#)) for at least 7 days prior to randomization
- I 10. Have been applying medium-potency TCS on all active AD lesions, once daily for at least 7 days before randomization, using the standardized regimen provided in the protocol.

Note: Low-potency TCS or topical calcineurin inhibitor (TCI) may be used on areas that cannot be safely treated with medium- potency TCS (eg, face, genital, flexural areas, or areas of skin atrophy)

I 11. Willing and able to comply with all clinic visits and study-related procedures

Weight

Not applicable.

Sex

Male or female

Informed Consent

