9.4.1 Efficacy analyses

Note: All daily assessments (eg, sleep NRS, actigraphy parameters, sleep diary, etc.) will be analyzed as weekly averages for the week immediately preceding the study visit. Thus, the baseline value will correspond to the assessments completed during the week preceding randomization.

Table 4 - Efficacy analyses

Endpoint	Statistical Analysis Methods
Primary Percent change from baseline to week 12 in sleep NRS	Percent change from baseline will be analyzed using a mixed effect model with repeated measures (MMRM) with treatment, baseline value, randomization stratum, week, treatment by week interaction, and baseline value by week interaction terms (all as fixed effects) in the model. An unstructured correlation matrix will be used to model the within-patient errors. No imputations for missing values will be carried out for the primary analysis. LS mean changes between the dupilumab group and placebo, the corresponding 95% CI of the differences and p-values will be provided.

Secondary

Change from baseline to week 12 in sleep efficiency, total sleep time, wake after sleep onset, sleep onset latency based on actigraph data

The similar approach as for the analysis of primary endpoint will be used.

A similar approach as for the analysis of primary endpoint will be used.

Percent change from baseline to week 12 in Pruritus NRS

A similar approach as for the analysis of primary endpoint will be used.

Change from baseline to week 12 in SCORing Atopic Dermatitis (SCORAD) total score

A similar approach as for the analysis of primary endpoint will be used.

Change from baseline to week 12 in SCORAD sleep VAS

A similar approach as for the analysis of primary endpoint will be used.

Change from baseline to week 12 in Dermatology Quality Life Index (DLQI)

A similar approach as for the analysis of primary endpoint will be used.

Change from baseline to week 12 in Patient Oriented Eczema Measure (POEM) total score

A similar approach as for the analysis of primary endpoint will be used.

Change from baseline to week 12 in PROMIS Sleep Related Impairment SF8a total score

Proportion of patients with EASI50, EASI75 (reduction of EASI score by $\geq 50\%$ and $\geq 75\%$ from baseline, respectively) at each time point

will be analyzed via the Cochran-mantel-Haenszel test adjusted by the randomization stratum at each time point

Exploratory

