During the beginning of the study the patients will be shown how to use the sleep watch. The participant will be instructed to wear the watch on the non-dominant wrist for 7 days 24 hour periods (minimum of 5 nights, including at least 1 weekend/non-work day period). The watch will be worn 7 evenings of sleep before each clinical visit. The participant also will be instructed on

completing a diary concurrently (see [Section 10.9](#), Appendix 9). This will provide a “backup” in case there are questions about the recording.

Steps to process actigraphy data and send them to the Reading Center are described in detail in a Site Coordinator Manual.

An actigraph log should be maintained at the clinic so that the locations of the Actiwatch devices are known at all times. A serial number (EX. A01785) for each Actiwatch can be found on the backside of each Actiwatch. This should be used as the Actiwatch ID.

QUALITY ASSURANCE FOR THE ACTIWATCH

Each research personnel charged with the responsibility of initializing, downloading or any other handling of the Actiwatch will be required to meet performance standards that indicate an understanding of the Actiwatch’s battery life, use of communications dock and software, and explaining the Actiwatch and sleep diary completion to the participant. Only personnel who meet these standards will be certified and approved to handle the Actiwatch devices and instruct the participants.

Personnel will be required to attend a training session, or undergo local training by a certified technician.

Training will consist of:

1. Overview of Actigraphy Operations Manual, including detailed use of Actiwatch, the software, and the communications dock
2. Hands on training for initializing and downloading/saving of files
3. Overview of Actiware Spectrum® Software Manual

[figure not shown]
CERTIFICATION

Each staff member handling the Actiwatch devices needs to successfully complete 3 initializations, downloading, file checking, and the saving to the assigned folder.

[figure not shown]

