- f) Sleep center will administer electrodes per American Academy of Sleep Medicine (AASM) criteria for a clinical sleep recording, including electroencephalogram, electrooculography, electromyography, ECG, electrodes for monitoring leg movements, airflow sensors and Respiratory Inductance Plethysmography sensors for monitoring breathing and O₂ saturation. Calibrations per SOP for the sleep center.
- g) Sleep center will begin sleep recording ~30 minutes prior to each individual patient's chosen sleep time.
- h) Sleep center will begin a video recording ~30 minutes prior to each individual patient's chosen sleep time.

B) Next day (and the third PSG night)

- a) Sleep recording will end after each individual patient's natural wake time.
- b) Video recording will end after each individual patient's natural wake time.
- c) Patients will continue to wear actiwatch and complete all patient reported outcomes in their iPad upon awakening for the day.
- d) Patients and study site will complete the remaining study related assessments as per the schedule of activities.

C) Within 2 business days

- a) Sleep center will send the EDF files or other agreed upon format of the PSG recordings to a blinded central reader site which will use AASM criteria to score by a registered PSG technician.
 - Reported outcomes include (but not limited to) sleep onset latency (SOL), wake after sleep onset (WASO), total sleep time (TST), longest sleep episode, stages of sleep, sleep efficiency and arousal index.
- b) If a patient has evidence of a clinical sleep disorder as detected by the PSG, the central reading PSG clinic will notify the PSG site the patient is from, and the PSG site will then notify the patient. That site will also be responsible for reporting this as an AE if relevant (ie, in case of worsening of frequency or severity of sleep disorder as compared to baseline status). These patients will continue in the main study unless their condition requires immediate attention or permanent or temporary discontinuation of the study for any safety reason.

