4.1. Sample Size

The sample size calculations were based on the subset of patients who reported ≥ 5 units of baseline sleep loss and ≥ 3 units of baseline pruritus scores on the SCORAD instrument in a previous study (AD1424) evaluating efficacy of dupilumab for AD.

Since no previous data are available on daily sleep on the NRS scale, the SCORAD sleep component (VAS) data was used as a basis for the sample size determination for the primary endpoint. The variability (standard deviation) estimate for the subset of patients mentioned above was 37% for the % change from baseline to week 12. Given the uncertainty in the variability from this variable to the NRS weekly average sleep score, the above variability was inflated by $\sim 20\%$, and assumed to be 44% for the primary sleep parameter. With these assumptions, a total sample of 150 (50 in placebo and 100 in dupilumab group) patients will provide 90% power ($\alpha = 0.05$, 2-sided) to detect a treatment difference of 25% (effect size, $\Delta/\sigma = 0.57$) for the percent change from baseline.

For secondary actigraphy endpoints, sample size estimates are provided in reference to Nemolizumab Ph2 data at week 4. For TST, to detect a 30 minutes difference between treatments: (2:1 allocation ratio; $\alpha=0.05$, 2-sided), assuming the same variability at week 16 weeks as seen for Nemolizumab at week 4 (=56 min), then 167 subjects are needed to provide 90% power. Furthermore, the proposed sample size would have $>90\%$ power to detect a difference of 10% for change from baseline in actigraphy based sleep efficiency, assuming a variability of 11% ($\alpha=0.05$, 2-sided). The variability estimate was based on for actigraphy based sleep efficiency at week 4, inflated by 50% to account for possible increase in variability over time (from week 4 to week 16). Of note, the data used for actigraphy parameters are limited.

Allowing for 20% dropouts, a total of approximately 201 patients will be enrolled in the study.

Considering the uncertainty of the variability of the primary endpoint, when data are available for this endpoint from about 50% of the patients completing Week 12, the variability will be assessed in a blinded manner, and the sample size will be re-estimated. If the re-estimated sample size is higher than the original estimate, the sample size may be increased accordingly, not to exceed a total of 150 additional patients.

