8.1.5. Sensitivity Analysis

If a specific weekly average for the sleep quality NRS was derived using 3 or less assessments, such assessments will be set to missing in any sensitivity analysis.

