day. The ESS score (the sum of 8 item scores, 0-3) can range from 0 to 24. The higher the ESS score, the higher that person's average sleep propensity in daily life, or their daytime sleepiness.

ESS score will be directly provided by KONEKSA.

Sleep Quality NRS

The Sleep Quality NRS is a simple assessment tool that patients will use to report the quality of patient's last night sleep. Patients will be asked the following question:

“On a scale of 0 to 10, with 0 being “worst possible sleep” and 10 being the “best possible sleep”, select the number that best describe the quality of your sleep last night”

Patients will complete the rating scale daily including 7 days immediately preceding the baseline visit (or daily for 5 days (from Day -7 to Day -3 prior to baseline) for patients participating in the PSG sub-study), and daily for 4 weeks (through visit 4), then daily during the week before each planned visit.

Instructions: Please complete the following question upon awakening for the day.

Select the number that best describe the quality of your sleep last night.

0	1	2	3	4	5	6	7	8	9	10	
Worst possible sleep											Best possible sleep

Patient chooses a value from 0 to 10 in the only question of the scale and that value is the global score of the scale.

Sleep Quality NRS score will be directly provided by KONEKSA.

Peak Pruritus NRS

The Peak Pruritus NRS is a simple assessment tool that patients will use to report the intensity of their pruritus (itch) during a daily recall period. Patients will be asked the following question:

“On a scale of 0 to 10, with 0 being ‘no itch’ and 10 being the ‘worst itch imaginable’ , how would you rate your itch at the worst moment during the previous 24 hours?”

Patients will complete the rating scale daily for 7 days prior to baseline (or daily for 5 days (from Day -7 to Day -3 prior to baseline) for patients participating in the PSG sub-study), and daily for 4 weeks (through visit 4), and then daily during the week before each planned visit.

On a scale of 0 to 10, with 0 being “no itch” and 10 being “worst itch imaginable”, how would you rate your itch at the worst moment during the previous 24 hours?

0	1	2	3	4	5	6	7	8	9	10
No itch										Worst itch imaginable

Patient chooses a value from 0 to 10 in the only question of the scale and that value is the global score of the scale.

Peak Pruritus NRS score will be directly provided by KONEKSA.

Skin Pain NRS

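### A patient can be randomised on a mean of 4 daily ratings, but the SAP needs at least 5 to form a baseline, so a patient with only 4 usable pre-baseline ratings drops out of the primary and first key secondary analyses

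*SAP*

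**What the plan says.** **Eligibility.** Protocol 5.1, criteria I 07 (peak pruritus NRS) and I 08 (sleep quality NRS), use the average over the 7 days before baseline, or over 5 days in the PSG sub-study, and state that "at least 4 ratings over the prior week/over the 5 days are required to calculate the average".

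**Analysis baseline.** SAP 4.4.6 sets a general rule (last valid value before randomisation and first dose) and then makes daily assessments an exception. Their baseline is the average of 7 consecutive days "or at least 5 days if data for 7 days were not available) prior to the Visit 1 Week 0 baseline visit", after Screening. Nothing is said about fewer than 5 days. Protocol 9.4.1 sets no minimum: "the baseline value will correspond to the assessments completed during the week preceding randomization".

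**Use of the baseline.** It is the denominator of the primary endpoint (SAP 8.1) and enters the MMRM as a main effect and by visit (SAP 8.1.1). Missing values are not imputed (SAP 8.1.3). The mITT set requires a baseline (SAP 4.3.3). Peak pruritus NRS is first in the secondary testing order (SAP 8.2.23).

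**Other minimums.** The sensitivity rule in SAP 8.1.5 applies "If a specific weekly average for the sleep quality NRS was derived using 3 or less assessments". Protocol Appendix 8 asks for a "minimum of 5 nights, including at least 1 weekend/non-work day period" for actigraphy.

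**PSG schedule.** SAP 15.8, like footnote d of the schedule of activities, has the sleep quality NRS completed "daily for 5 days (from Day -7 to Day -3 prior to baseline) for patients participating in the PSG sub-study"; the same applies to peak pruritus. Protocol Appendix 10 has patients, on the morning after a PSG night, "complete all patient reported outcomes in their iPad upon awakening for the day".

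**The concern.** The same ratings serve two purposes under two different minimums, and the stricter one applies after the patient has been randomised. A patient whose 4-rating mean was good enough to qualify can be left without a baseline for the endpoint the trial was designed around.

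Nothing in the documents explains the stricter figure. SAP section 13 describes the revision of this baseline definition only as a way to include one patient whose ratings ran from Day -13 to Day -7. A rule reworked to keep one patient still shuts out others whom the protocol accepted.

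The PSG stratum may be the most exposed. Only 5 ratings are scheduled there, so if nothing else counts, a single missed entry removes an eligible patient. Appendix 10 may add ratings after the PSG nights on Day -2 and Day -1, and the SAP window would admit them, but the documents do not say whether they are meant to count.

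**Working it through.** **1. The texts side by side.** The eligibility minimum is 4 and the baseline minimum is 5. With exactly 4 usable ratings between Screening and Visit 1, I 07 and I 08 can be met, but the condition in SAP 4.4.6 fails and the last-value rule is excluded. Percent change cannot be computed, and the model covariate is missing. Table 3.1.2 and the sample code name ITT, while SAP section 8 and Appendix 15.1 name mITT; the patient drops out of the model either way.

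**2. The plan's own power.** Protocol 9.2 gives difference 25, SD 44, two-sided alpha 0.05 and 100 versus 50 patients. A two-sample t-test gives power of 0.903, so the stated 90% reproduces.

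**3. Reference without this loss.** SAP 4.1 says: "Allowing for 20% dropouts, a total of approximately 201 patients will be enrolled in the study". 201 × 0.8 = 160.8 patients at 2:1, for which the same test gives 92.2%.

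**4. Chance of exactly 4 ratings, given eligibility.** No completion rate is given, so daily completion p is assumed to be 0.95, 0.90 or 0.85, independent across days. With X binomial(n, p), the share is P(X = 4) / P(X ≥ 4).

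| | p = 0.95 | p = 0.90 | p = 0.85 |
|---|---|---|---|
| n = 7 (non-PSG) | 0.0036 | 0.0230 | 0.0624 |
| n = 5 (PSG) | 0.208 | 0.357 | 0.469 |

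For n = 5 and p = 0.95 this is 5 × 0.95⁴ × 0.05 / (5 × 0.95⁴ × 0.05 + 0.95⁵) = 0.25 / (0.25 + 0.95) = 0.208.

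**5. Expected patients without a baseline.** With about 30 PSG patients, 201 − 30 = 171 are non-PSG. If m PSG mornings count (m = 0, 1 or 2), a PSG patient with 4 scheduled ratings is lost only if all m are also missed:

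loss = 171 × share(n = 7) + 30 × share(n = 5) × (1 − p)^m

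At p = 0.90 and m = 0: 3.94 + 10.71 = 14.65.

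**6. Power.** Evaluable N = (201 − loss) × 0.8, with the same t-test.

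| PSG mornings counted | Loss of 201 (p = 0.95 / 0.90 / 0.85) | Power, % |
|---|---|---|
| none | 6.9 / 14.7 / 24.7 | 91.3 / 90.1 / 88.5 |
| one | 0.9 / 5.0 / 12.8 | 92.0 / 91.5 / 90.4 |
| both | 0.6 / 4.0 / 11.0 | 92.1 / 91.6 / 90.7 |

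If dropout instead uses up the whole margin down to 150 evaluable, the starting power is 90.3%. Applying the first-row losses in proportion, N = 150 × (1 − loss/201), gives 89.3 / 88.0 / 86.2%.

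These counts sit at the upper end. They allow no rating outside the scheduled days other than the PSG mornings, and no effect of the missed-entry alerts to sites (Protocol 8.1.2).

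**The case against.** **A stricter analysis minimum can be deliberate.** Eligibility only checks a cut-off, whereas the baseline is a denominator and a covariate, and 5 days matches the actigraphy minimum. That would be defensible if stated, but no reason is given, and the price is validly randomised patients. The noise argument is small: see the cost under the fix.

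**The SAP does not say that such a patient has no baseline.** A programmer might fall back on the last available value. But the general rule is expressly subject to the exception for daily scales, and the fallback would give a single-night baseline, worse than the 4-day mean it replaces.

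**The SAP window is wider than the eligibility week.** A patient with 4 ratings in that week may have enough earlier ones after Screening. This stands: the point applies only to a patient with 4 usable pre-baseline ratings in total.

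**SAP 8.1.5 concerns a sensitivity analysis of weekly averages.** This also stands. It supports the view that 4 ratings are thought adequate, but proves nothing about the baseline.

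**The harm is small.** In 8 of the 9 scenarios in the main table power stays at or above 90%. PSG sites must compute the 5-day means before any PSG procedure, so gaps there should be noticed. No document shows that an affected patient exists, and SAP 5.1 already tabulates the analysis sets and lists exclusions. This limits the size of the problem but does not remove the mismatch.

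**Conclusion.** The point holds. The 4-versus-5 mismatch is in the text and depends on no assumption. For a patient with only 4 usable ratings before Visit 1, it means exclusion from the primary and first key secondary models under either analysis set.

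The harm is a modest loss of completeness and precision, possibly concentrated in the PSG stratum. It is not a bias between arms, since the loss is determined before randomisation. Its size is uncertain because it rests on an assumed completion rate, on independent days with equal completion in every stratum, and on how the PSG mornings are treated. It should be fixed before database lock because the fix is cheap and the question of who has a baseline should not be left until after unblinding.

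**What to change.** 1. In SAP 4.4.6 keep the window as it is (after Screening and before Visit 1, so the patient rated from Day -13 to Day -7 stays in). Change only the minimum: at least 4 days for sleep quality NRS and peak pruritus NRS, and at least 5 for the other daily assessments, including actigraphy.
2. State whether ratings made on the mornings after the baseline PSG nights count, reconciling footnote d of the schedule of activities and SAP 15.8 with Protocol Appendix 10.
3. Record the change in SAP section 13.
4. Report the number of randomised patients without a baseline for each of the two scales, by arm and randomisation stratum.

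The cost is one clause, one sentence on the PSG mornings, one line in section 13 and one disposition row; SAP section 1 provides for revisions before database lock. The statistical price is a noisier baseline in the few patients with 4 ratings: with independent days, its standard error is √(5/4) = 1.12 times that of a 5-rating mean.
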